## 5 Modeling Details

Recall at the first stage the groups are clustered according to a Dirichlet Process Mixture Model.

The number of clusters is not assumed to be known in advance but will instead be inferred from the data using Dirichlet Process Mixtures (DPM). The DPM looks across all the possible clusterings of the groups and assigns a probability to each based on the data. The prior distribution in a DPM is governed by a parameter  $\alpha$ . When  $\alpha$  is small, the prior favors large clusters. As  $\alpha$  tends to zero, the prior tends to place all its mass on a single cluster containing all the groups. As  $\alpha$  increases, the prior places more mass on clusterings with a large number of clusters. As  $\alpha$  becomes very large, the prior places all of its mass on having a separate cluster for each group (that is, no borrowing across groups). Thus, by specifying extreme values of the prior one could force the groups into one cluster or force the groups to be analyzed in separate clusters. Here we choose a moderate version of  $\alpha=2$  (common values might be anywhere between 0.5 and 5) and allow the data more control over the clustering.

The details of the prior are as follows. Let  $z_g$  represent the cluster to which group  $g$  belongs. Then  $z_g \sim \text{Categorical}(\mathbf{p})$ , where  $\mathbf{p}$  is the vector such that  $p_k$  is the probability that a group belongs to cluster  $k$  and  $\sum_{k=1}^{\infty} p_k = 1$ . We construct  $\mathbf{p}$  using a stick-breaking process:

$$p_k = \beta_k \prod_{i=1}^{k-1} (1 - \beta_i)$$

and

$$\beta_k \sim \text{Beta}(1, \alpha).$$

A large value of  $\alpha$  thus removes a very small amount of probability for  $\mathbf{p}$ , resulting in many clusters, while a small value of  $\alpha$  tends to produce probabilities near 1 for the first cluster.

Conditional on the clustering, we fit a hierarchical model which has an across groups distribution

$$\theta_g \sim N(\mu, \tau^2)$$

As discussed above, this across groups distribution states that within a cluster we expect to see some variation in the parameters, with that variation governed by  $\tau$ . When  $\tau$  is small, there is minimal variation across groups within a cluster, and thus within the cluster the model would approach pooling. In contrast, when  $\tau$  is large we expect large amount of across group variation, and thus even though the groups are in the same cluster the  $\theta_g$  values may be quite different. Apriori we have no way of knowing  $\tau$ , so we estimate it using the data combined with the prior distributions

$$\mu \sim N(0, 1.82)$$

and

$$\tau^2 \sim IG(3,0.5),$$

where  $IG(\alpha, \beta)$  is the inverse gamma distribution defined by:

$$f(x|\alpha, \beta) = \frac{\beta^\alpha e^{-\beta/x}}{x^{\alpha+1} \Gamma(\alpha)}.$$

When the entire model is implemented (via Markov Chain Monte Carlo) we consider the full joint distribution of the clustering combined with the hierarchical model parameters. We average over the entire range of the uncertainty in the parameters to produce the posterior distribution for each group parameter  $\theta_g$ , which is then used to drive the decisions in the model.

8.5	Modeling Details	30
9	References	32

1 Introduction

The primary efficacy variable, clinical benefit rate, will be analyzed by a Novartis designated Contract Research Organization (CRO), [REDACTED]. Analysis details are provided in Appendix R of the protocol, which is also included in Section 8 of this Report Analysis Plan (RAP).

[REDACTED]
[REDACTED]
All other data will be analyzed by a different Novartis-designed CRO, [REDACTED] according to Section 10 of the study protocol which will be available in Appendix 16.1.1 of the Clinical Study Report (CSR). Important information is given in the following sections and details will be provided, as applicable, in Appendix 16.1.9 of the CSR. All statistical analyses will be performed using SAS® Version 9.3 (or higher).

2 Statistical and analytical plans

2.1 Study design

This is a phase II, open label study to determine the efficacy and safety of treatment with ribociclib (LEE011) in patients with solid tumors or hematological malignancies that have been pre-identified as having CDK4/6, cyclin D1/3, or p16 aberrations and whose disease has progressed on or after standard treatment. Pre-identification of the relevant gene mutation or amplification status will be performed locally at a Clinical Laboratory Improvement Amendments (CLIA) certified laboratory prior to participation on the trial.

To be eligible for enrollment to this study, patients must have archival tissue available for submission to allow for molecular testing related to pathway activation. If tissue is not available or is insufficient the patient must be willing to undergo a fresh tumor biopsy to allow for these analyses. Mutation types from both local and central laboratories will be analyzed.

Patients must have received at least one prior treatment for their recurrent, metastatic and/or locally advanced disease and have no remaining standard therapy options anticipated to result in a durable response. Patients received ribociclib on a flat scale of 600 mg once daily, 3 weeks on and 1 week off. A complete treatment cycle is defined as 28 days. Patients may continue on study treatment until disease progression, withdrawal of consent, unacceptable toxicity, death, or any other reasons (e.g., physician's decision). The patient may not receive any additional anti-cancer therapy during treatment with ribociclib. After discontinuation of study treatment, patients, regardless of reason for study treatment discontinuation, will be followed for safety for 30 days after the last dose. Survival information will be collected every 3 months until 2 years after the last patient has enrolled in the study regardless of treatment discontinuation reason (except if consent is withdrawn). If the study's primary efficacy endpoint is not met, Novartis may decide not to conduct survival follow up for the study.

2.2 General overview of statistical methodology

Data from all centers that participate in this protocol will be used. Data used for the analyses specified in this document will come from the Electronic Data Capture (EDC) system. In addition, the mutation data from the central laboratory will be collected in an Excel spreadsheet format and subsequently be uploaded to a secure FTP site by Novartis.

The analyses stated in this document will be based on all patients' data up to the time when all patients have had the opportunity to complete at least 4 cycles (or 16 weeks) of study treatment or discontinued study. The data cut-off date will be the date when the last patient on treatment completes 4 cycles of study treatment. This will be the cut-off point for the clinical study report (CSR). Additional data for patients continuing to receive study treatment beyond the data cut-off date for the primary CSR will be reported once all patients have discontinued treatment or been lost to follow-up.

All statistical analyses presented in this document are related to patient background information, efficacy, and safety. All analyses are descriptive and no hypothesis testing is planned (except for the primary efficacy variable, which is described in Section 8 below). For continuous data, the mean, standard deviation (SD), median, 25th and 75th percentiles, minimum, and maximum will be presented. For categorical data, frequencies and percentages will be presented. In general, data from all centers will be combined for any analysis. There will be no stratification factor considered for the analysis with the exception of tumor type in the primary efficacy variable analyses. Missing data will not be imputed. All data collected in the study will be presented in the listings.

The primary efficacy objectives of the study, clinical benefit (e.g., for solid tumor – CR, PR, stable disease [SD] \geq 16 weeks) associated with ribociclib treatment based on local investigator assessment, will be analyzed by using a Bayesian hierarchical model for evaluation of trial success and futility, and the relationship between pathway activation and response (if applicable). Analysis details are documented in Section 8.

In addition, with all solid tumor types combined and separately for each hematological tumor type, the clinical benefit rate (CBR) will be provided with its 95% exact confidence interval (CI) (using clopper-pearsone¹ method); overall response rate (ORR, e.g., partial response [PR] and complete response [CR] for solid tumor) and its 95% CI will be presented. Summary on numbers and percentages of patients for each response category (e.g., for solid tumor - CR, PR, stable disease [SD], progressive disease [PD], not evaluable [NE]) will also be provided. For tumor types that have ten (10) or more patients, separate summaries will be performed by the tumor type using the same methodology. In the event that there are fewer than 4 patients for a hematological tumor type, only listing will be provided.

Duration of response (DOR) based on local investigator assessment will also be analyzed. Progression-free survival (PFS) and overall survival (OS) will be summarized using Kaplan-Meier (KM) methodology.

Patient demographics, disease characteristics (including mutation analyses), ribociclib treatment, and safety variables will be analyzed descriptively.

Details of the above analyses are presented in the following sections.

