## **Amendment 3 (10-Apr-2017)**

Study CLEE011XUS03 was initiated in August 2014 and closed to enrollment on May 8, 2015 with 106 patients enrolled. As of April 6, 2017, one patient remains on study.

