## **Amendment 2**

Study CLEE011XUS03 was initiated in August 2014 and as of April 2nd, 2015, a total of 78 patients have been dosed.

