## Figure 4-1 Study Start-up Design

#### **4.1.1 Treatment phase**

Patients will continue to receive study treatment until disease progression (assessed by investigator per RECIST 1.1 or appropriate hematologic response criteria), unacceptable toxicity, death or discontinuation from study treatment for any other reason (e.g., withdrawal of consent, start of a new anti-neoplastic therapy or at the discretion of the investigator), otherwise known as End of Treatment. All patients who discontinue from study treatment due to disease progression must have their progression clearly documented.

Disease assessments (per RECIST 1.1 or appropriate hematological response criteria) will be performed every 8 weeks ( $\pm 4$  days) after first dose of study drug (Day 1 of every odd cycle), until disease progression or end of treatment, whichever occurs first. The frequency of disease assessment will be reduced to every 16 weeks after patients have completed 16 weeks on treatment. Scans will be assessed locally by the investigator.

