#### **4.2 Definition of end of the study**

End of study is defined as the time when the last patient completes the survival follow-up as described in [Section 7.1.4.3](#), when the last patient on study has died, been lost to follow up, or withdraws consent, whichever occurs first, or if the study is terminated early or another clinical study becomes available that can continue to provide LEE011 in this patient population and all patients ongoing are eligible to be transferred to that clinical study.

The analysis of study data will be based on all patients' data up to the time when all patients have had the opportunity to complete at least 4 cycles (or 16 weeks) of treatment or discontinued the study. This will be the cut-off point for the clinical study report (CSR). Additional data for patients continuing to receive study treatment past the data cutoff date for the CSR will be reported once all patients have discontinued treatment or been lost to follow-up.

At the time of CSR data cut-off, if patients are ongoing after 16 weeks on treatment and benefitting, they will continue to receive treatment.

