### 7.2.1.1 Solid Tumors

Response will be evaluated, using modified Response Evaluation Criteria in Solid Tumors, based on RECIST 1.1. For complete details, refer to [Appendix B](#).

Clinical evaluation and tumor assessments will be performed as is indicated in [Table 7-1](#), based on physical examination and radiological evaluation. For solid tumors, an assessment of PR or greater based on RECIST 1.1 must be confirmed at least 4 weeks after initial observation. If the two assessments differ, the best overall response will be determined by [Table 3-3 of Appendix B](#).

Any lesion that has been previously treated with radiotherapy should be considered as a non-target lesion. However, if a lesion previously treated with radiotherapy has clearly progressed since the radiotherapy, it can be considered as a target lesion.

If the measurable disease is restricted to a solitary lesion, its neoplastic nature should be confirmed by cytology/histology.

Definitions for measurable and non-measurable lesions, and criteria for response, should be based on RECIST 1.1 ([Appendix B](#)).

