4.1 Clinical Benefit Rate (CBR)

Clinical benefit is determined by investigator assessment for each tumor assessment and is defined as responses of CR or PR or SD for ≥ 16 weeks. In addition to tumor-specific measurements (e.g., radiological assessment of tumor response for solid tumors), progressive disease will also be considered when it was indicated either as a reason for the study treatment

discontinuation or as a cause of on-treatment death. CR and PR (for solid tumors) require a confirmation that is at least a minimum of 4 weeks after the initial observation of response. Patients who had confirmed CR/PR or SD prior to 16 weeks, but discontinued prior to 16 weeks for reasons other than progressive disease, will have their clinical benefit defined as non-evaluable; patients who had confirmed CR/PR or SD prior to 16 weeks, but progressed prior to 16 weeks, will be considered as not achieving clinical benefit; patients who had CR/PR/SD occurred prior to 16 weeks, but progressed at or after 16 weeks without evidence of CR/PR/SD at or after 16 weeks, will also be considered as not achieving clinical benefit. CBR will be analyzed by comparing achieved CBR with a historical control rate of each tumor type, and if there is at least 80% probability that the response rate in a tumor type exceeds the historical rate, then the tumor type will be considered a success. Details for the Bayesian analyses of CBR are located in Section 8.

In addition to the Bayesian analyses, with all solid tumor types combined and separately for each hematological tumor type, the CBR estimate will be provided with its 95% exact CI. For tumor types (within the solid tumors) that have ten (10) or more patients, separate summaries will be performed by the tumor type. In the event that there are fewer than 4 patients for a hematological tumor type, only listing will be provided for that tumor type.

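### The CSR data cut-off (Day 112 of the last on-treatment patient) makes no allowance for that patient's week-16 scan window or for confirming a response first seen on that scan

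*SAP*

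**What the plan says.** Under Protocol 4.2, before the data are closed for the CSR, everyone must "have had the opportunity to complete at least 4 cycles (or 16 weeks) of treatment or discontinued the study". It gives no exact date. SAP 2.2 does: "The data cut-off date will be the date when the last patient on treatment completes 4 cycles of study treatment". The same paragraph applies this cut-off to the analyses in the SAP generally, and says later data on patients who continue treatment will be reported once everyone is off treatment or lost.

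Protocol 4.1.1 sets an 8-week interval between disease assessments, with a window of ±4 days. Their timing is given as "after first dose of study drug (Day 1 of every odd cycle), until disease progression or end of treatment, whichever occurs first". Protocol 7.1.2 sets 28-day cycles counted from Cycle 1 Day 1. After week 16 the scan interval lengthens to 16 weeks.

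On confirmation, Protocol 7.2.1.1 says: "For solid tumors, an assessment of PR or greater based on RECIST 1.1 must be confirmed at least 4 weeks after initial observation". SAP 4.1 repeats the requirement. Under Appendix B Table 3-3, a PR followed by a non-evaluable time point becomes SD if the minimum SD duration is met, and otherwise non-evaluable.

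SAP 4.1 defines clinical benefit as CR, PR or SD lasting at least 16 weeks. Patients who stop before week 16 for reasons other than progression are non-evaluable. Those who progress before week 16 are failures. So are those with an earlier response or SD "but progressed at or after 16 weeks without evidence of CR/PR/SD at or after 16 weeks".

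SAP 8.1.2 places the final Bayesian analysis after the CSR analysis. SAP 8.3.3 places it when accrual and follow-up are complete in all groups.

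**The concern.** The cut-off is tied to completing treatment cycles, whereas the primary endpoint depends on a scan scheduled for the next day, with a window running 4 days beyond that. For the last patients on treatment, the rule can close the data before the assessment that decides SD of at least 16 weeks.

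The exposure is one-sided. Only patients still on drug at week 16 are at risk, and they are the ones most likely to have benefit. SAP 4.1 gives no outcome for such a patient: still on treatment, SD at week 8, no week-16 scan, neither progressed nor discontinued. SAP 2.2 rules out imputation.

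The same rule leaves no time to confirm a response first seen on the week-16 scan. That bears on the key secondary endpoint (ORR), the response categories and DOR.

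**Working it through.** **Inputs.** Cycle length 28 days from Day 1 (Protocol 7.1.2). Scans on Day 1 of odd cycles, ±4 days (Protocol 4.1.1). Confirmation at least 28 days later (Protocol 7.2.1.1, SAP 4.1). One week = 7 days (SAP 2.5.8). Accrual: "a total of 78 patients have been dosed" as of April 2, 2015 (Amendment 2), and the study "closed to enrollment on May 8, 2015 with 106 patients enrolled" (Amendment 3).

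**The plan's own figure.** 4 × 28 = 112 days, and 112 / 7 = 16.0 weeks. The equation of 4 cycles with 16 weeks is reproduced.

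**Week-16 scan.** Cycle 5 Day 1 = 4 × 28 + 1 = Day 113, window 113 ± 4 = Days 109-117. Of these 9 compliant days, 4 (Days 109-112) fall on or before the cut-off and 5 (Days 113-117) fall after it.

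**Does an early-window scan count?** Day 109 is 109 / 7 = 15.6 weeks counting Day 1, and Day 112 is 16.0. By elapsed time, Day 112 is 111 / 7 = 15.9 weeks and Day 113 is 112 / 7 = 16.0. On a strict reading, Days 109-111 precede week 16 and Day 112 qualifies only if Day 1 is counted. The SAP does not settle this.

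**Earliest confirmation of a response first seen at week 16.**

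| Scan day | Earliest confirmation | Days after cut-off |
|---|---|---|
| 109 | 137 | 25 |
| 113 | 141 | 29 |
| 117 | 145 | 33 |

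The next scheduled scan is 113 + 112 = Day 225.

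**Who is exposed.** A patient first dosed *k* days before the last on-treatment patient is at Day 112 + *k* at cut-off.
- On-schedule scan missed: 113 > 112 + *k*, so *k* = 0 only.
- Late-window scan missed: 117 > 112 + *k*, so *k* = 0-4 (5 entry days).
- On-schedule scan, confirmation missed: 141 > 112 + *k*, so *k* = 0-28 (29 entry days).

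**How many (assumption: even entry, enrolled treated as dosed).**
- Low rate: 106 patients over the 280 days from August 1, 2014 (the day in August is assumed) to May 8, 2015 = 0.38 per day.
- High rate: (106 − 78) / 36 days = 0.78 per day.
- Scan at risk: 5 × 0.38 = 1.9 to 5 × 0.78 = 3.9, so about 2-4 entrants.
- Confirmation at risk: 29 × 0.38 = 11 to 29 × 0.78 = 23 entrants.

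These count entrants. Assume 24% to 50% are still on treatment at week 16; the lower figure is the phase I proportion with SD of at least 4 cycles (Protocol 1.2.1.2.2), and the upper is a judgement. Then about 0.5-2 patients have a scan at risk and about 3-11 could have a new response left unconfirmed. Using the phase I rate of 3 PRs in 114 evaluable patients (2.6%) as a rough guide, 11 to 23 entrants yield about 0.3 to 0.6 responses at any time, and fewer first seen at week 16.

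**What one patient could do in a small cohort.** This illustration uses an independent flat prior, not the trial's model, with a control rate of 0.45. With 6 benefits in 10, the posterior probability of exceeding control is 0.83. It is 0.63 if one benefit is scored as failure (5/10) and 0.74 if that patient is dropped (5/9). Both fall below the 0.80 success line.

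**The case against.** The strongest reply is that the plan does not force any loss. The window opens on Day 109, so the last patient can be scanned compliantly by Day 112. Completing 4 cycles might also be read as reaching the Cycle 5 Day 1 visit, which removes the gap for an on-schedule scan. Both points stand. They limit the claim to patients who may lack the scan, but they do not cover late-window scans or confirmation, or say whether an early scan satisfies the 16-week condition.

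A reader might infer that the confirmation gap also depresses the primary endpoint. It does not if SD has lasted 16 weeks: the unconfirmed PR becomes SD, which is clinical benefit. The effect falls on ORR, the response categories and DOR, all descriptive, and SAP 7 attaches no power consideration to secondary objectives.

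A reader might also infer that the per-cohort success calls rest on truncated data. The documents do not establish this. SAP 8.1.2 and 8.3.3 put the final Bayesian analysis after the CSR analysis and at complete follow-up, and SAP 2.2 promises later data on continuing patients. But SAP 2.2 also applies its cut-off to the SAP's analyses without excepting Section 8, so the sections conflict and the question is open.

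Finally, the accrual rate mixes patients dosed with patients enrolled. The glossary sets enrollment at consent, so some of the last 28 may have consented before April 2. The counts are orders of magnitude only.

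**Conclusion.** The timing defect holds and follows directly from the documents: the cut-off is Day 112, the scan is due on Day 113 with a window to Day 117, and confirmation of an on-schedule week-16 response is possible from Day 141.

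For CBR, exposure is confined to patients first dosed within about 4 days of the last on-treatment patient: roughly 2-4 entrants, perhaps 0.5-2 still on treatment, and then only if scanned after the cut-off. The SAP has no rule for classifying them. For ORR, roughly 11-23 entrants fall in the confirmation gap, but only those with a new response at week 16 are affected, probably 0-1. It would be wrong to read the 11-23 as patients harmed.

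These sizes rest on even accrual at 0.38-0.78 per day, enrollment standing in for first dose, 24-50% on treatment at week 16, and a phase I response rate. The effect on the success calls cannot be determined until the SAP says which data the final analysis uses. The point is moderate: small in expected size, but it concerns the primary endpoint in small cohorts and is cheap to remove.

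**What to change.** 1. In SAP 2.2 and Protocol 4.2, define the CSR cut-off as the date when every patient still on treatment has had the Cycle 5 Day 1 disease assessment or its window has closed (Day 117, +5 days), extended to allow confirmation of any CR or PR first seen on that scan (up to Day 145, +33 days). Day 145 is the earliest confirmation after a last-window scan. The plan sets no upper limit for confirmation, so the text should name the date after which an unconfirmed response is scored as such.
2. In SAP 4.1, state that an in-window week-16 scan (Days 109-117) counts as the 16-week assessment, and say how a patient still on treatment without one at cut-off is classified.
3. Reconcile SAP 2.2 with 8.1.2 and 8.3.3 on which data the final CBR analysis uses, and carry the answer into Protocol Appendix R.

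The cost is a change of wording and a CSR cut-off later by 5 days (CBR only) to about 5 weeks (with confirmation). It needs no added patients or procedures.
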